APPENDIX 1 MANAGEMENT ALGORITHMS

These general guidelines constitute guidance to the investigator and may be supplemented by discussions with the Medical Monitor representing the Sponsor. The guidance applies to all immuno-oncology (I-O) agents and regimens.

A general principle is that differential diagnoses should be diligently evaluated according to standard medical practice. Non-inflammatory etiologies should be considered and appropriately treated.

Corticosteroids are a primary therapy for I-O drug-related adverse events (AE). The oral equivalent of the recommended intravenous doses may be considered for ambulatory patients with low-grade toxicity. The lower bioavailability of oral corticosteroids should be taken into account when switching to the equivalent dose of oral corticosteroids.

[figure not shown]
Consultation with a medical or surgical specialist, especially prior to an invasive diagnostic or therapeutic procedure, is recommended.

The frequency and severity of the related AEs covered by these algorithms will depend on the I-O agent or regimen being used.

Figure 1: Gastrointestinal Adverse Event Management Algorithm

Rule out non-inflammatory causes. If non-inflammatory cause is identified, treat accordingly and continue I-O therapy. Opiates/narcotics may mask symptoms of perforation. Infliximab should not be used in cases of perforation or sepsis.

Patients on IV steroids may be switched to an equivalent dose of oral corticosteroids (eg, prednisone) at start of tapering or earlier, once sustained clinical improvement is observed. Lower bioavailability of oral corticosteroids should be taken into account when switching to the equivalent dose of oral corticosteroids.

ADL = activities of daily living; CTCAE = Common Terminology Criteria for Adverse Events; IV = intravenous; NCI = National Cancer Institute.

[figure not shown]
Source: Appendix 3, BMS936558 IB v15

Revised Protocol No.: 12

Date: 08-May-2018

Figure 2: Renal Adverse Event Management Algorithm

Rule out non-inflammatory causes. If non-inflammatory cause, treat accordingly and continue I-O therapy.

Patients on IV steroids may be switched to an equivalent dose of oral corticosteroids (eg, prednisone) at start of tapering or earlier, once sustained clinical improvement is observed. Lower bioavailability of oral corticosteroids should be taken into account when switching to the equivalent dose of oral corticosteroids. CTCAE = Common Terminology Criteria for Adverse Events; IV = intravenous; NCI = National Cancer Institute; ULN = upper limit of normal.

[figure not shown]
Source: Appendix 3, BMS936558 IB v15

Revised Protocol No.: 12

Date: 08-May-2018

Figure 3: Pulmonary Adverse Event Management Algorithm

Rule out non-inflammatory causes. If non-inflammatory cause, treat accordingly and continue I-O therapy. Evaluate with imaging and pulmonary consultation.

Patients on IV steroids may be switched to an equivalent dose of oral corticosteroids (eg, prednisone) at start of tapering or earlier, once sustained clinical improvement is observed. Lower bioavailability of oral corticosteroids should be taken into account when switching to the equivalent dose of oral corticosteroids. CTCAE = Common Terminology Criteria for Adverse Events; ID = infectious disease; IV = intravenous; NCI = National Cancer Institute.

[figure not shown]
Source: Appendix 3, BMS936558 IB v15

Revised Protocol No.: 12

Date: 08-May-2018

Figure 4: Hepatic Adverse Event Management Algorithm

Rule out non-inflammatory causes. If non-inflammatory cause, treat accordingly and continue I-O therapy. Consider imaging for obstruction.

Patients on IV steroids may be switched to an equivalent dose of oral corticosteroids (eg, prednisone) at start of tapering or earlier, once sustained clinical improvement is observed. Lower bioavailability of oral corticosteroids should be taken into account when switching to the equivalent dose of oral corticosteroids.

***I-O therapy may be delayed rather than discontinued if AST/ALT ≤ 8 × ULN and total bilirubin ≤ 5 × ULN.**

****The recommended starting dose for Grade 4 hepatitis is 2 mg/kg/day methylprednisolone IV.**

ALT = alanine aminotransferase; AST = aspartate aminotransferase; BID = twice daily; CTCAE = Common Terminology Criteria for Adverse Events; IV = intravenous; LFT = liver function test; NCI = National Cancer Institute; ULN = upper limit of normal.

[figure not shown]
Source: Appendix 3, BMS936558 IB v15

Revised Protocol No.: 12

Date: 08-May-2018

Figure 5: Endocrinopathy Management Algorithm

Rule out non-inflammatory causes. If non-inflammatory cause, treat accordingly and continue I-O therapy. Consider visual field testing, endocrinology consultation, and imaging.

Patients on IV steroids may be switched to an equivalent dose of oral corticosteroids (eg, prednisone) at start of tapering or earlier, once sustained clinical improvement is observed. Lower bioavailability of oral corticosteroids should be taken into account when switching to the equivalent dose of oral corticosteroids.

IV = intravenous; MRI = magnetic resonance imaging; PO = oral; TSH = thyroid stimulating hormones; ULN = upper limit of normal.

[figure not shown]
Source: Appendix 3, BMS936558 IB v15

Revised Protocol No.: 12

Date: 08-May-2018

Figure 6: Skin Adverse Event Management Algorithm

Rule out non-inflammatory causes. If non-inflammatory cause, treat accordingly and continue I-O therapy.

Patients on IV steroids may be switched to an equivalent dose of oral corticosteroids (eg, prednisone) at start of tapering or earlier, once sustained clinical improvement is observed. Lower bioavailability of oral corticosteroids should be taken into account when switching to the equivalent dose of oral corticosteroids.

*Refer to NCI CTCAE v4 for term-specific grading criteria.

^If SJS/TEN is suspected, withhold I-O therapy and refer patient for specialized care for assessment and treatment. If SJS or TEN is diagnosed, permanently discontinue I-O therapy.

BSA = body surface area; CTCAE = Common Terminology Criteria for Adverse Events; IV = intravenous; NCI = National Cancer Institute; SJS = Stevens Johnson Syndrome; TEN = toxic epidermal necrolysis.

[figure not shown]
Source: Appendix 3, BMS936558 IB v15

Revised Protocol No.: 12

Date: 08-May-2018

Figure 7: Neurological Adverse Event Management Algorithm

Rule out non-inflammatory causes. If non-inflammatory cause, treat accordingly and continue I-O therapy.

Patients on IV steroids may be switched to an equivalent dose of oral corticosteroids (eg, prednisone) at start of tapering or earlier, once sustained clinical improvement is observed. Lower bioavailability of oral corticosteroids should be taken into account when switching to the equivalent dose of oral corticosteroids. ADL = activities of daily living; CTCAE = Common Terminology Criteria for Adverse Events; IV = intravenous; IVIG = intravenous immunoglobulin therapy; NCI = National Cancer Institute; PO = oral.

Source: Appendix 3, BMS936558 IB v15

Revised Protocol No.: 12

Date: 08-May-2018

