3.5 Discontinuation of Subjects from Treatment

Subjects MUST discontinue investigational product (and non-investigational product at the discretion of the investigator) for any of the following reasons:

- Withdrawal of informed consent (subject's decision to withdraw for any reason)
- Any clinical AE, laboratory abnormality, clinical deterioration, or concurrent illness that in the opinion of the investigator indicates that continued participation in the study is not in the best interest of the subject
- Pregnancy
- Termination of the study by BMS
- Loss of ability to freely provide consent through imprisonment or involuntary incarceration for treatment of either a psychiatric or physical (eg, infectious disease) illness

- Documented and confirmed irPD as defined by irRECIST for the Dose Escalation and Cohort Expansion (Part 1; completed) and the SCCHN Cohort Expansion (Part 2; completed) (see [Appendix 2](#)).
- Documented PD for the SCCHN Randomized Cohorts (Part 3), and the Signal Detection in SCCHN with Lirilumab, Nivolumab, and Ipilimumab Combination (Part 5) as defined by RECIST v1.1 (see [Appendix 3](#)).
- Documented and confirmed irCR as defined by irRECIST for the Dose Escalation and Cohort Expansion (Part 1; completed) and the SCCHN Cohort Expansion (Part 2; completed) (see [Appendix 2](#)).
- Documented and confirmed CR for the Signal Detection in SCCHN with Lirilumab, Nivolumab, and Ipilimumab Combination (Part 5) as defined by RECIST v1.1 (see [Appendix 3](#)).
- Discretion of the investigator
- Inability to comply with the protocol requirements
- Protocol defined reasons for discontinuation (see [Section 4.9.5](#))
- Maximum treatment duration of up to a maximum of 2 years; 12 cycles in Parts 1, 2, and 3 or 8 cycles in Part 5.

In the case of pregnancy, the investigator must immediately notify the Sponsor or designee of this event. In most cases, the study drug will be permanently discontinued in an appropriate manner (eg, dose tapering if necessary for subject safety). Please contact the Sponsor or designee within 24 hours of awareness of the pregnancy. If the investigator determines a possible favorable benefit/risk ratio that warrants continuation of study drug, a discussion between the investigator and the Sponsor or designee must occur.

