4.9.5 Guidelines for Permanent Discontinuation

Subjects will be required to permanently discontinue all study drugs for the following AEs:

- 1) Any Grade 2 drug-related uveitis, eye pain, or blurred vision that does not respond to topical therapy and does not improve to Grade 1 severity within the retreatment period OR requires systemic treatment
 - 2) For subjects receiving lirilumab in combination with nivolumab or nivolumab monotherapy (the Dose Escalation and Cohort Expansion [Part 1; completed] and the SCCHN Cohort Expansion [Part 2; completed], the SCCHN Randomized Cohorts [Part 3],): Any Grade 3 non-skin, drug-related AE lasting > 7 days or recurs, with the following exceptions for laboratory abnormalities, drug-related uveitis, pneumonitis, bronchospasm, hypersensitivity reactions, infusion reactions, and endocrinopathies:
 - a) Grade 3 drug-related uveitis, pneumonitis, bronchospasm, hypersensitivity reaction, or infusion reaction of any duration requires discontinuation.
 - b) Grade 3 drug-related endocrinopathies, adequately controlled with only physiologic hormone replacement, do not require discontinuation. Adrenal insufficiency requires discontinuation regardless of control with hormone replacement.
 - c) Grade 3 drug-related laboratory abnormalities do not require treatment discontinuation except:
 - i) Grade 3 drug-related thrombocytopenia > 7 days or associated with bleeding
 - ii) Grade ≥ 3 drug-related AST, ALT, or total bilirubin*
 - iii) Concurrent AST or ALT > $3 \times$ ULN and total bilirubin > $2 \times$ ULN
- * In most cases of Grade 3 AST or ALT elevation, study drug(s) will be permanently discontinued. If the investigator determines a possible favorable benefit/risk ratio that warrants continuation of study drug(s), a discussion between the investigator and the BMS Medical Monitor/designee must occur.
- 3) For subjects receiving lirilumab in combination with nivolumab and ipilimumab (the Signal Detection in SCCHN with Lirilumab, Nivolumab, and Ipilimumab Combination [Part 5]): Any Grade 3 non-skin, drug-related AE lasting > 7 days, or recurs with the following exceptions for laboratory abnormalities, diarrhea, colitis, neurologic toxicity, drug-related uveitis, pneumonitis, bronchospasm, hypersensitivity reactions, infusion reactions, and endocrinopathies:

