 - a) Grade 3 drug-related diarrhea, colitis, neurologic toxicity, uveitis, pneumonitis, bronchospasm, hypersensitivity reaction, or infusion reaction of any duration requires discontinuation.
 - b) Grade 3 drug-related endocrinopathies, adequately controlled with only physiologic hormone replacement, do not require discontinuation. Adrenal insufficiency requires discontinuation regardless of control with hormone replacement.

- c) Grade 3 drug-related laboratory abnormalities do not require treatment discontinuation except:
 - iv) Grade 3 drug-related thrombocytopenia > 7 days or associated with bleeding
 - v) Any drug-related liver function test abnormality that meets the following criteria:
 - (1) Grade ≥ 3 drug-related AST, ALT, or total bilirubin*
 - (2) Concurrent AST or ALT > $3 \times$ ULN and total bilirubin > $2 \times$ ULN

* In most cases of Grade 3 AST or ALT elevation, study drug(s) will be permanently discontinued. If the investigator determines a possible favorable benefit/risk ratio that warrants continuation of study drug(s), a discussion between the investigator and the BMS Medical Monitor/designee must occur.

- 4) Any Grade 4 drug-related AE or laboratory abnormality (including but not limited to creatinine, AST, ALT, or total bilirubin), except for the following events, which do not require discontinuation:
 - a) Isolated Grade 4 electrolyte imbalances/abnormalities that are not associated with clinical sequelae and are corrected with supplementation/appropriate management within 72 hours of their onset
 - b) Grade 4 neutropenia ≤ 7 days
 - c) Grade 4 lymphopenia or leukopenia or asymptomatic amylase or lipase
 - d) Grade 4 lymphopenia < 5 days in duration
 - e) Grade 4 drug-related endocrinopathy AEs, such as hyper- or hypothyroidism, or glucose intolerance, which resolve or are adequately controlled with physiologic hormone replacement (corticosteroids or thyroid hormones) or glucose-controlling agents, respectively, may not require discontinuation after discussion with and approval from the BMS Medical Monitor.
- 5) Any DLT as outlined in [Section 4.8](#) will require permanent discontinuation with the following exceptions:
 - a) Grade 3 diarrhea, nausea, vomiting, or abdominal pain that returns to Grade 1 or baseline within 3 days with medical intervention
 - b) Grade 3 ALT or AST that returns to Grade 1 or baseline within 7 days with medical intervention

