6.8 Treatment Algorithms for Drug-related Adverse Events

Treatment algorithms for the management of potential drug-related AEs are located in [Appendix 1](#) of this protocol and in the IB for nivolumab.¹⁹

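### The visible Appendix 1 hepatic footnote allows a dose delay at combined AST/ALT and bilirubin values for which Section 4.9.5 requires a permanent stop, and no text says which one governs

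*Protocol*

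**What the plan says.** **Appendix 1, Figure 4 (hepatic algorithm), footnote:** "I-O therapy may be delayed rather than discontinued if AST/ALT ≤ 8 × ULN and total bilirubin ≤ 5 × ULN". The footnote sets upper limits only and makes no separate provision for concurrent elevation. The introduction to the appendix describes its status: "These general guidelines constitute guidance to the investigator".

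**Section 4.9.5:** the lead sentence is mandatory: "Subjects will be required to permanently discontinue all study drugs for the following AEs". For the doublet and monotherapy parts, item 2c(iii) lists "Concurrent AST or ALT" above 3 × ULN with total bilirubin above 2 × ULN. For the triplet in Part 5, item 3c(v)(2) gives the same pair of thresholds under "Any drug-related liver function test abnormality that meets the following criteria". An asterisk on the neighbouring Grade 3-or-higher line leads to a note: "In most cases of Grade 3 AST or ALT elevation, study drug(s) will be permanently discontinued". That note allows continuation after a discussion with the Medical Monitor.

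**End of Section 4.9.5:** a general route lets therapy be re-initiated after an event that met the permanent-stop criteria. Investigator and Sponsor must both support it, and details must go to the FDA or another health authority beforehand.

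**Section 3.5:** the list of reasons for which subjects must stop includes "Protocol defined reasons for discontinuation", with a reference to 4.9.5.

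**Section 6.8:** "Treatment algorithms for the management of potential drug-related AEs are located in" Appendix 1 and in the nivolumab IB. It says nothing about what happens if these differ from 4.9.5.

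**The concern.** A site managing a liver event would naturally open the hepatic algorithm, because Section 6.8 sends it there. Read as printed, the footnote lets the site hold drug and keep the subject eligible for more. For part of the range it covers, Section 4.9.5 calls for a permanent stop. A site that delays in that range commits a protocol deviation on a safety rule while following text in the same protocol.

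The values matter clinically. They meet the aminotransferase and bilirubin thresholds of the general potential-DILI definition in Section 6.6, which also has cholestasis and alternative-cause conditions. Part 5 is the first evaluation of the three-drug combination (Section 1.5), and Revised Protocol 12 lets subjects with continuing benefit stay on treatment.

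**Working it through.** No sample size, power or error rate is involved. The check compares two threshold regions and then reads each possible exception.

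**Inputs (multiples of ULN)**

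| Text | AST/ALT | Total bilirubin | Action |
|---|---|---|---|
| Appendix 1 hepatic footnote | ≤ 8 | ≤ 5 | delay permitted |
| 4.9.5 items 2c(iii), 3c(v)(2), drug-related | > 3 | > 2 | permanent stop |

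**Overlap.** Intersecting the two rows gives AST/ALT in (3, 8] with bilirubin in (2, 5].

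**Examples.** Drug-related ALT 7 × with bilirubin 4 ×: 3 < 7 ≤ 8 and 2 < 4 ≤ 5, so both rows apply. ALT 4 × with bilirubin 2.5 ×: 3 < 4 ≤ 8 and 2 < 2.5 ≤ 5, so both rows apply again.

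**Does an exception in 4.9.5 reconcile them?**

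1. The asterisk sits on the Grade 3-or-higher line, and its text concerns Grade 3 AST or ALT elevation. It is not attached to the concurrent criterion.
2. The exceptions in item 5, such as Grade 3 ALT or AST that recovers within 7 days, qualify the DLT stop only. They do not qualify items 2c or 3c.
3. The re-initiation route at the end of 4.9.5 does reach this event. It needs Sponsor agreement and advance submission to a health authority, so it is a different procedure from a delay at the site's choice.

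**What do the neighbouring sections say?**

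- Section 4.9.3 refers to 4.9.5 for subjects who must stop and lets only the others resume. It also sends Grade 3-or-higher AST, ALT and bilirubin to discontinuation.
- Section 4.9.4 says combined Grade 2 AST/ALT and bilirubin values that meet the discontinuation parameters should lead to a permanent stop.
- The 4.9.3 liver bullet and the 4.9.4 combined bullet both cite Section 4.8, which is declared not applicable from Amendment 13. Section 4.8.2 carries the same 3 × and 2 × thresholds, so the intent is clear, but the live rule is in 4.9.5.

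**Frequency.** The documents give no count of concurrent elevations. The nearest figure, in Section 1, is AST increased in 4 of 322 subjects, listed after the related Grade 3 or 4 total: 4/322 = 1.24%, printed as 1.2%. It does not count this event.

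**The case against.** The strongest reply is that nothing needs reconciling. Appendix 1 is generic guidance for all immuno-oncology regimens, taken from the nivolumab IB, and its footnote is permissive. Section 4.9.5 is specific to this study and mandatory, and Section 3.5 reinforces it. The delay, resumption and stop sections all lead to discontinuation, and a site that stops complies with every text. This stands as a reason for low severity, and it makes the intended precedence easy to infer. It does not make the texts consistent. The footnote is worded as an alternative to stopping, and no sentence ranks the two sources.

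A second reply is that the body of Figure 4 is not shown. The row that the footnote belongs to, and any condition printed there, cannot be checked; a condition on concurrent elevation would narrow or remove the overlap. This also stands. The point therefore covers the footnote text alone and does not extend to the algorithm as a whole.

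Two stronger readings are tempting. A reader might infer that a concurrent elevation ends treatment with no way back; the re-initiation route in 4.9.5 shows otherwise. A reader might also infer that 4.9.4 leaves higher grades uncovered because its combined bullet names Grade 2. It does not, since 4.9.3 and 4.9.5 already require discontinuation for Grade 3 or higher liver tests, subject to the Medical Monitor note for Grade 3 AST or ALT.

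**Conclusion.** The point holds as a minor inconsistency in a stated dosing rule. For drug-related AST/ALT above 3 and up to 8 × ULN with bilirubin above 2 and up to 5 × ULN, the visible footnote permits a delay where 4.9.5 requires a permanent stop. Confidence is medium because the figure body is missing.

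The practical reach is small. Enrollment is closed, treatment is capped at 2 years, and potential DILI must be reported as an SAE under Section 6.6. Only subjects still on treatment could be affected. No endpoint, sample size or analysis changes. The documents do not show that any subject was dosed contrary to 4.9.5, and nothing here should be read as saying so.

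**What to change.** Three edits in one protocol revision or administrative letter:

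1. Section 6.8, add: *Where Appendix 1 or the IB algorithms differ from Section 4.9.5, Section 4.9.5 governs.* This also covers the IB, which a footnote edit alone would not reach.
2. Appendix 1 hepatic footnote, add: *Does not apply to concurrent AST or ALT > 3 × ULN and total bilirubin > 2 × ULN, for which study drug is permanently discontinued per Section 4.9.5; for Grade 3 AST or ALT alone, the Medical Monitor discussion in Section 4.9.5 is required.*
3. Change the Section 4.8 references to Section 4.9.5 in the Grade 3-or-higher liver bullet of 4.9.3 and in the combined AST/ALT and bilirubin bullet of 4.9.4.

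The cost is two added sentences and two corrected cross-references. No procedures, visits or subjects are added.

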4.9.3 Dose Delays Due To Toxicity

Subjects who experience a DLT must have therapy held. Subjects who are required to permanently discontinue study drug administration are listed in [Section 4.9.5](#). All other subjects will be permitted to resume study drug administration at the same doses for all study drugs following resolution of the AE to Grade 1 or less, or to baseline.

Study drug administration should be delayed for the following:

- Grade 2 non-skin, drug-related AE, with the exception of fatigue
- Grade 2 drug-related creatinine, AST, ALT, and/or total bilirubin abnormalities
- Grade 3 skin, drug-related AE
- Grade 3 drug-related laboratory abnormality, with the following exceptions:
 - Grade 3 lymphopenia or asymptomatic amylase or lipase does not require dose delay
 - Grade ≥ 3 AST, ALT, and total bilirubin will require dose discontinuation (see [Section 4.8](#))
- Any AE, laboratory abnormality, or intercurrent illness, which, in the judgment of the investigator, warrants delaying the dose of study drug

Subjects who require delay of nivolumab should be re-evaluated weekly or more frequently if clinically indicated and resume nivolumab dosing when retreatment criteria are met.

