4.9.4 Criteria for Subsequent Dosing

Subsequent dosing may continue if subjects continue to meet laboratory criteria as listed in [Section 3.3.1](#). The investigator will determine if subsequent dosing is appropriate for subjects who have laboratory or clinical abnormalities that do not meet DLT (Section 4.8) or discontinuation criteria (Section 4.9.5). All related Grade 2 toxicities should be discussed with the BMS Medical Monitor prior to subsequent dosing.

Subjects may resume treatment with study drug when the drug-related AE(s) resolve to Grade ≤ 1 or baseline value, with the following exceptions:

- Subjects may resume treatment in the presence of Grade 2 fatigue.
- Subjects who have not experienced a Grade 3 drug-related skin AE may resume treatment in the presence of Grade 2 skin toxicity.
- For subjects with Grade 2 AST, ALT, and/or total bilirubin abnormalities, dosing may resume when laboratory values return to baseline and management with corticosteroids, if needed, is complete.
- Subjects with combined Grade 2 AST/ALT and total bilirubin values meeting discontinuation parameters (Section 4.8) should have treatment permanently discontinued.
- Drug-related pulmonary toxicity, diarrhea, or colitis must have resolved to baseline before treatment is resumed. Subjects with persistent Grade 1 pneumonitis after completion of a steroid taper over at least 1 month may be eligible for retreatment if discussed with and approved by the BMS Medical Monitor.

- Subjects with drug-related endocrinopathies adequately controlled with only physiologic hormone replacement may resume treatment after consultation with the BMS Medical Monitor. Adrenal insufficiency requires discontinuation regardless of control with hormone replacement.

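### For a diagnosed, drug-related SJS/TEN graded 3, no item in Section 4.9.5 clearly requires a permanent stop on diagnosis or grade alone, while the Appendix 1 skin algorithm says to stop permanently

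*Protocol*

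**What the plan says.** Two parts of the protocol bear on Stevens-Johnson syndrome (SJS) and toxic epidermal necrolysis (TEN).

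**Appendix 1, Figure 6 (skin algorithm), footnote.** On suspicion, withhold therapy and refer. On diagnosis: "If SJS or TEN is diagnosed, permanently discontinue I-O therapy". No grade is attached. The introduction to Appendix 1 describes the algorithms as guidance to the investigator, and Section 6.8 says where they are found. Section 1.5 commits the sponsor to training sites on them.

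**Sections 4.9.3 to 4.9.5 (dosing rules).**
- Section 4.9.3 makes Section 4.9.5 the list of mandatory stops: "Subjects who are required to permanently discontinue study drug administration are listed in" that section. It continues: "All other subjects will be permitted to resume study drug administration at the same doses for all study drugs", once the event has resolved to Grade 1 or less or to baseline. Its list of reasons to delay includes "Grade 3 skin, drug-related AE".
- Section 4.9.4 leaves events that meet neither the DLT nor the discontinuation criteria to the investigator: "The investigator will determine if subsequent dosing is appropriate". Its one skin provision is "Subjects who have not experienced a Grade 3 drug-related skin AE may resume treatment in the presence of Grade 2 skin toxicity".
- Section 4.9.5 sets the Grade 3 stop for Parts 1 to 3 in item 2 as "Any Grade 3 non-skin, drug-related AE lasting > 7 days or recurs", and item 3 uses the same non-skin limit for Part 5. Item 3a then names events that stop treatment at once: "Grade 3 drug-related diarrhea, colitis, neurologic toxicity, uveitis, pneumonitis, bronchospasm, hypersensitivity reaction, or infusion reaction of any duration requires discontinuation".

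**The concern.** For a serious skin reaction, the section a site consults to decide on re-dosing gives a less protective answer than the sponsor's own algorithm. After a resolved Grade 3 case, the algorithm forbids re-dosing and the dosing section permits it.

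A second safeguard is weakened too. Section 4.9.5 requires details to go to health authorities before study therapy is re-initiated, but only where the event meets the criteria for permanent discontinuation. An event that is not clearly on that list does not clearly trigger the submission.

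The event is not purely theoretical for these drugs. Section 1.1.4.1 reports a death involving TEN in another study (CA209012, original nivolumab plus ipilimumab groups). That was not the Part 5 regimen, and the text does not present it as a case of re-dosing.

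**Working it through.** No figure in the plan is at issue. The check is to take one event, a diagnosed and drug-related SJS/TEN graded 3, through each rule.

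**Section 4.9.5, item by item**

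| Item | Trigger | Does it require a stop on diagnosis or Grade 3 alone? |
|---|---|---|
| 1 | Grade 2 uveitis, eye pain or blurred vision | No |
| 2 | Grade 3 non-skin event (Parts 1, 2, 3) | No. Item 2a names uveitis, pneumonitis, bronchospasm, hypersensitivity reaction and infusion reaction; none is a skin event |
| 3 | Grade 3 non-skin event (Part 5) | No. Item 3a adds diarrhea, colitis and neurologic toxicity; none is a skin event |
| 4 | Grade 4 drug-related event | No at Grade 3; yes at Grade 4 |
| 5 | Any DLT under Section 4.8 | Unclear (see below) |
| 6 | Delay over 6 weeks from the previous dose | No. It depends on the length of the delay, and prolonged steroid tapers are exempt |
| 7 | Substantial clinical risk in the investigator's judgment | No. It depends on that judgment |

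**Item 5.** Section 4.8.3 counts a Grade 3 non-hepatic, non-hematologic toxicity as a DLT, and SJS/TEN is not among its exceptions. Exception 5c, for Grade 3 rash or pruritus that settles within 7 days, shows that item 5 was meant to reach skin events. But Section 4.8 confines itself to Parts 1 and 2 and states that it and its subsections have not applied since Amendment 13. On the other side, item 5 is still printed without a not-applicable label, and Sections 4.9.3 and 4.9.4 still refer to DLTs and to Section 4.8. Its status is ambiguous.

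**Sections 4.9.3 and 4.9.4.** An event not caught by 4.9.5 falls among the other subjects who may resume. Grade 3 skin events are listed as a delay. Section 4.9.4 allows resumption at Grade 1 or lower or baseline; a previous Grade 3 skin event removes only the option of resuming at Grade 2 skin toxicity.

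**Side by side**

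| Text | Outcome for a confirmed Grade 3 case |
|---|---|
| Sections 4.9.3/4.9.4 | Delay, then resumption permitted, subject to items 6 and 7, Section 3.5 and investigator or Medical Monitor review |
| Appendix 1, Figure 6 footnote | Permanent discontinuation |

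No text says which prevails.

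**The case against.** The strongest reply is that the protocol already states the rule. The footnote is specific, resumption under 4.9.3/4.9.4 is general and only permitted, and Section 9.1.1 requires conduct as described in the protocol, which includes its appendices. A site that stops breaches nothing. This stands, and it is why the point is minor. It does not remove the inconsistency: Appendix 1 is labelled guidance, 4.9.5 is the list that 4.9.3 points to, and 4.9.5 names other serious reactions such as pneumonitis and bronchospasm without leaving them to an appendix.

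A reader might go further and infer that such a subject faces no mandatory stop at all. The documents do not support that. Item 6 requires discontinuation after a delay over 6 weeks unless an exception applies, and item 6c requires Medical Monitor consultation before restarting after such a delay. Item 7 and Section 3.5 require discontinuation once the investigator makes the judgment they describe. Section 4.9.4 also asks for Medical Monitor discussion of related Grade 2 toxicities before further dosing; it would be odd to read that as exempting worse ones. An event meeting the seriousness criteria must be reported to the sponsor within 24 hours.

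A reader might also infer that item 5 is certainly dead, or that it only ever covered the 56-day DLT window. Neither is safe. Item 5 is still printed, and the synopsis says that, for subject management, DLTs lead to interruption whatever the cycle. That sentence does not settle the matter the other way: it speaks of interruption, not permanent discontinuation, and it sits in a synopsis paragraph itself marked as not applicable since Amendment 13.

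Finally, SJS/TEN might be treated as a hypersensitivity reaction under items 2a and 3a. A site could do so, but the sponsor places it in the skin algorithm, and both items open with a non-skin limit.

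**Conclusion.** The point holds as a minor inconsistency in a safety stopping rule. For a diagnosed, drug-related SJS/TEN graded 3, no item in Section 4.9.5 clearly requires a permanent stop on the diagnosis or grade alone, and 4.9.3/4.9.4 permit resumption that the Appendix 1 footnote rules out. The plan does not compel re-dosing, and other stops and reviews remain.

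The conclusion rests on these limits:
- That a case can be graded 3 is an assumption, because CTCAE grading is not in the documents. If every case is graded 4, item 4 closes the gap.
- The boxes of Figure 6 are not shown, so the branch the footnote belongs to is unseen.
- SJS and TEN are taken together because the footnote does so.
- A separately reported eye event or Grade 3 non-skin event could still meet items 1 to 3 in its own right.

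No frequency can be derived: the documents give neither an SJS/TEN incidence nor the number of subjects still on treatment. Exposure is limited, since enrollment is closed and treatment is capped at 2 years, but subjects with clinical benefit remain on study drug. No endpoint or analysis is affected.

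**What to change.** Carry the Appendix 1 rule into the dosing section.

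- In 4.9.5 add: *Confirmed SJS or TEN: permanently discontinue all study drugs, irrespective of grade.*
- In 4.9.3 add: *Suspected SJS/TEN: withhold all study drugs.*
- In 4.9.4 except confirmed SJS/TEN from resumption.

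Saying all study drugs matters, because 4.9.5 otherwise lets nivolumab continue when only lirilumab or ipilimumab meets the criteria. Listing the event in 4.9.5 also brings any proposed re-initiation under the existing health-authority review and removes the dependence on item 5. The cost is three lines in a protocol clarification, with no effect on sample size, endpoints or analysis.
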